9.2.2 Metabolic Change

In addition to mean change from baseline, incidence of treatment emergent significant changes in fasting lipids, fasting glucose, and metabolic syndrome will be summarized by parent study treatment group using the following criteria.

Criteria for Treatment-Emergent Significant Change in Lipids and Glucose		
LAB PARAMETER	BASELINE ¹	ANYTIME POST BASELINE
LDL Direct, Fasting (MG/DL)	Borderline 100-<160	High ≥ 160
	Normal/Borderline <160	High ≥ 160
	Normal <100	Borderline/High ≥ 100
	Any Value	Increased ≥ 30
HDL Cholesterol, Fasting (MG/DL)	Normal ≥ 40	Low <40
	Any Value	Decreased ≥ 20
Triglycerides, Fasting (MG/DL)	Normal <150	High 200-<500
	Borderline 150-<200	High 200-<500
	Normal/Borderline <200	High 200-<500
	Normal <150	Borderline/High/Very High ≥ 150
	Any Value	Increased ≥ 50
Glucose Fasting, Serum (MG/DL)	Normal <100	High ≥ 126
	Impaired 100-<126	High ≥ 126
	Normal/Impaired <126	High ≥ 126
	Any Value	Increased ≥ 10

¹ BASELINE IS DEFINED AS THE LAST AVAILABLE MEASUREMENT PRIOR TO THE FIRST DOSE OF OPEN-LABEL IMP IN THE OPEN-LABEL TREATMENT PHASE.

Criteria for Treatment-Emergent Metabolic Syndrome	
DESCRIPTION	ANYTIME POST BASELINE ¹
Central Obesity	Waist Circumference $\geq 102\text{cm}(\text{MALE}), \geq 88\text{cm}(\text{FEMALE})$
Dyslipidemia	Triglycerides $\geq 150\text{mg/dl}$
Dyslipidemia	HDL $< 40\text{mg/dl}(\text{MALE}), < 50\text{mg/dl}(\text{FEMALE})$
Supine Blood Pressure	Systolic $\geq 130\text{mmHg}$ and Diastolic $\geq 85\text{mmHg}$

Criteria for Treatment-Emergent Metabolic Syndrome	
DESCRIPTION	ANYTIME POST BASELINE¹
Glucose Fasting, Serum	$\geq 100\text{mg/dl}$
Metabolic Syndrome	Met 3 Or More of the Above Criteria at a Visit

¹ BASELINE IS DEFINED AS THE LAST AVAILABLE MEASUREMENT PRIOR TO THE FIRST DOSE OF OPEN-LABEL IMP IN THE OPEN-LABEL TREATMENT PHASE.

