4.5 Definition of Completed Subjects

The treatment period is defined as the time period during which subjects are evaluated for primary and/or secondary objectives of the trial irrespective of whether or not the subject actually consumed all doses of the IMP. Subjects who are evaluated at the last scheduled visit during the treatment period will be defined as trial completers. For purposes of this trial, subjects who complete Week 12 visit will be defined as trial completers.

5 Trial Population

The trial population will consist of eligible male and female subjects diagnosed with BPD and who, in the investigator's judgment, could potentially benefit from treatment with brexpiprazole for BPD according to the following criteria:

- Subjects who participated in a double-blind brexpiprazole BPD trial will be eligible for Trial 331-201-00195 if they have completed the last scheduled treatment visit of the previous double-blind trial and did not terminate early.
- Subjects must qualify for Trial 331-201-00195 at the last scheduled treatment visit of the previous double-blind trial and must be able to continue treatment without interruption between the double-blind and open-label trials (if a subject is unable to rollover immediately, up to 3 days may be permitted between the end of the double-blind trial and the start of IMP in the open-label extension trial; however, this must be discussed with the medical monitor).

Decisions regarding inclusion of subjects at the time of enrollment and assessment of subject safety throughout the trial primarily remain at the discretion of the investigator; however, the medical monitor may recommend exclusion or discontinuation of a subject based on individual subject data.

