10.5 Appendix 5: Criteria for Identifying Laboratory Values of Potential Clinical Relevance

Laboratory Tests	Criteria
Chemistry	
AST (SGOT)	$\geq 3 \times \text{ULN}$
ALT (SGPT)	$\geq 3 \times \text{ULN}$
Alkaline phosphatase	$\geq 3 \times \text{ULN}$
Lactate dehydrogenase	$\geq 3 \times \text{ULN}$
Blood urea nitrogen	$\geq 30 \text{ mg/dL}$
Creatinine	$\geq 2.0 \text{ mg/dL}$
Uric acid	
Men	$\geq 10.5 \text{ mg/dL}$
Women	$\geq 8.5 \text{ mg/dL}$
Bilirubin (total)	$\geq 2.0 \text{ mg/dL}$
Creatine phosphokinase	$> 3 \times \text{ULN}$
Prolactin	$> \text{ULN}$
Hematology	
Hematocrit	
Men	$\leq 37\% \text{ and decrease of } \geq 3 \text{ percentage points from baseline}$
Women	$\leq 32\% \text{ and decrease of } \geq 3 \text{ percentage points from baseline}$
Hemoglobin	
Men	$\leq 11.5 \text{ g/dL}$
Women	$\leq 9.5 \text{ g/dL}$
WBC count	$\leq 2,800 \text{ mm}^3 \text{ or } \geq 16,000 \text{ mm}^3$
Eosinophils	$\geq 10\%$
Neutrophils	$\leq 15\%$
Absolute neutrophil count	$\leq 1,500/\text{mm}^3$
Platelet count	$\leq 75,000/\text{mm}^3 \text{ or } \geq 700,000/\text{mm}^3$
Urinalysis	
Protein	Increase of ≥ 2 units
Glucose	Increase of ≥ 2 units
Casts	Increase of ≥ 2 units
Additional Criteria	
Chloride	$\leq 90 \text{ mEq/L} \text{ or } \geq 118 \text{ mEq/L}$
Potassium	$\leq 2.5 \text{ mEq/L} \text{ or } \geq 6.5 \text{ mEq/L}$
Sodium	$\leq 126 \text{ mEq/L} \text{ or } \geq 156 \text{ mEq/L}$
Calcium	$\leq 8.2 \text{ mg/dL} \text{ or } \geq 12 \text{ mg/dL}$
Glucose	
Fasting	$\geq 100 \text{ mg/dL}$
Nonfasting	$\geq 200 \text{ mg/dL}$
Total cholesterol, fasting	$\geq 240 \text{ mg/dL}$
LDL cholesterol, fasting	$\geq 160 \text{ mg/dL}$
HDL cholesterol, fasting	
Men	$< 40 \text{ mg/dL}$
Women	$< 50 \text{ mg/dL}$
Triglycerides, fasting	$\geq 150 \text{ mg/dL}$

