Appendix 2 Criteria for Identifying Laboratory Values of Potential Clinical Relevance

Laboratory Tests		Criteria
Chemistry		
AST (SGOT)		$\geq 3 \times$ upper limit of normal (ULN)
ALT (SGPT)		$\geq 3 \times$ ULN
Alkaline phosphatase		$\geq 3 \times$ ULN
Lactate dehydrogenase (LDH)		$\geq 3 \times$ ULN
Blood urea nitrogen (BUN)		≥ 30 mg/dL
Creatinine		≥ 2.0 mg/dL
Uric Acid		
Men		≥ 10.5 mg/dL
Women		≥ 8.5 mg/dL
Bilirubin (total)		≥ 2.0 mg/dL
Creatine phosphokinase (CPK)		$\geq 3 \times$ ULN
Prolactin		$>$ ULN
Hematology		
Hematocrit		
Men		$\leq 37\%$ and decrease of ≥ 3 percentage points from Baseline
Women		$\leq 32\%$ and decrease of ≥ 3 percentage points from Baseline
Hemoglobin		
Men		≤ 11.5 g/dL
Women		≤ 9.5 g/dL
White blood count		$\leq 2,800/\text{mm}^3$ or $\geq 16,000/\text{mm}^3$
Eosinophils		$\geq 10\%$
Neutrophils		$\leq 15\%$
Absolute neutrophil count		$\leq 1,500/\text{mm}^3$
Platelet count		$\leq 75,000/\text{mm}^3$ or $\geq 700,000/\text{mm}^3$
Urinalysis		
Protein		Increase of ≥ 2 units
Glucose		Increase of ≥ 2 units
Casts		Increase of ≥ 2 units
Additional Criteria		
Chloride		≤ 90 mEq/L or ≥ 118 mEq/L
Potassium		≤ 2.5 mEq/L or ≥ 6.5 mEq/L
Sodium		≤ 126 mEq/L or ≥ 156 mEq/L
Calcium		≤ 8.2 mg/dL or ≥ 12 mg/dL
Glucose		
Fasting		≥ 100 mg/dL
Non-Fasting		≥ 200 mg/dL
Total Cholesterol, Fasting		≥ 240 mg/dL
LDL Cholesterol, Fasting		≥ 160 mg/dL
HDL Cholesterol, Fasting		
Men		< 40 mg/dL
Women		< 50 mg/dL
Triglycerides, Fasting		≥ 150 mg/dL

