- CT-8.8.2 Listing of Serious TEAEs or Deaths that Are Related or Probably Related to COVID-19 (Safety Sample)
- CT-8.9 Incidence of Treatment-Emergent Adverse Events of Special Interests (AESIs) by System Organ Class and MedDRA Preferred Term (Safety Sample)
- CT-9.1 Listing of Deaths
- CT-9.2 Listing of Serious Adverse Events
- CT-9.3 Listing of Discontinuations Due to Adverse Events
- CT-10.1 Criteria for Laboratory Test Values with Potential Clinical Relevance
- CT-10.2.1 Listing of Laboratory Test Values with Potential Clinical Relevance by Subject (Safety Sample)
- CT-10.2.2 Listing of Laboratory Test Values with Potential Clinical Relevance by Test (Safety Sample)
- CT-10.2.3 Incidence of Laboratory Test Values with Potential Clinical Relevance (Safety Sample)
- CT-10.3.1 Mean Change from Baseline in Clinical Laboratory Test Results - Serum Chemistry (Safety Sample)
- CT-10.3.2 Mean Change from Baseline in Clinical Laboratory Test Results - Hematology (Safety Sample)
- CT-10.3.3 Mean Change from Baseline in Clinical Laboratory Test Results - Urinalysis (Safety Sample)
- CT-10.3.4 Mean Change from Baseline in Clinical Laboratory Test Results - Prolactin, by Sex (Safety Sample)
- CT-10.3.5 Mean Change from Baseline in Clinical Laboratory Test Results - Other Tests (Safety Sample)
- CT-10.4.1 Incidence of Laboratory Test Values with Potential Clinical Relevance - Prolactin (Safety Sample)
- CT-10.4.2 Listing of Laboratory Test Values with Potential Clinical Relevance - Prolactin (Safety Sample)
- CT-10.5.1.1 Incidence of Treatment-Emergent Significant Change in Lipids (Safety Sample)
- CT-10.5.1.2 Listing of Treatment-Emergent Significant Change in Lipids (Safety Sample)
- CT-10.5.2.1 Incidence of Treatment-Emergent Significant Change in Glucose (Safety Sample)
- CT-10.5.2.2 Listing of Treatment-Emergent Significant Change in Glucose (Safety Sample)
- CT-10.5.3.1 Incidence of Treatment-Emergent Metabolic Syndrome (Safety Sample)

- CT-10.5.3.2 Listing of Treatment-Emergent Metabolic Syndrome (Safety Sample)
- CT-10.6 Incidence of Potentially Liver Injury Related Laboratory Test Abnormalities (Safety Sample)
- CT-10.7 Listing of Potentially Liver Injury Related Laboratory Test Abnormalities (Safety Sample)
- CT-11.1 Criteria for Potentially Clinically Relevant Abnormalities in Vital Signs
 - CT-11.2.1 Listing of Potentially Clinically Relevant Abnormalities in Vital Signs (Safety Sample)

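### The treatment-emergent HDL shift row in SAP 9.2.2 uses 40 mg/dL for both sexes although the plan elsewhere calls a woman's HDL low below 50, so no planned categorical output gives new-onset low HDL in women at the plan's own cut-off

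*SAP*

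**What the plan says.** SAP 9.2.2 lists the criteria for treatment-emergent significant change in lipids and glucose. HDL has two rows, neither split by sex. The first is a shift: "HDL Cholesterol, Fasting (MG/DL) Normal ≥ 40 Low <40". The second is a decrease of 20 mg/dL or more from any baseline value. Baseline is the last measurement before the first open-label dose. The results go into CT-10.5.1.1, "Incidence of Treatment-Emergent Significant Change in Lipids (Safety Sample)", and the listing CT-10.5.1.2.

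Three other places define low HDL, and all three use below 40 mg/dL for men and below 50 mg/dL for women:

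- the metabolic-syndrome table, also in SAP 9.2.2;
- SAP Appendix 2, under "HDL Cholesterol, Fasting", which feeds CT-10.2.3, "Incidence of Laboratory Test Values with Potential Clinical Relevance (Safety Sample)", and the listings CT-10.2.1 and CT-10.2.2;
- Protocol Appendix 5 (Section 10.5), under "HDL cholesterol, fasting".

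Neither document explains the difference. Both sexes are enrolled (Protocol Section 5): "The trial population will consist of eligible male and female subjects diagnosed with BPD". The share of women is not stated.

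**The concern.** For women, the same blood value carries two labels. An HDL of 45 mg/dL is low in Appendix 2 and in the metabolic-syndrome component, but normal in the shift row. This has two consequences in CT-10.5.1.1:

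- **Missed onset.** A woman who goes from 50 or more to between 40 and 50 becomes low by the plan's other criteria, yet the shift row reads her as normal throughout.
- **Misattributed onset.** A woman who starts between 40 and 50 sits in the normal-at-baseline denominator. If she then falls below 40, she is reported as newly low although the plan's other criteria had her low already.

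A treatment-emergent table exists to separate new findings from findings already present. That matters here because subjects arrive from double-blind trials and results are shown by parent-study treatment group. Some may therefore reach the open-label baseline after weeks on brexpiprazole.

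**Working it through.** The plan states no HDL rate, sample size or sex mix, so there is no figure to reproduce. The check has a logical part, which needs no assumptions, and a sensitivity part, which rests wholly on assumptions.

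**1. Logical check.** Let B be baseline and F the post-baseline fasting HDL in mg/dL. Shift row: B >= 40 and F < 40. Decrease row: B - F >= 20. New onset at the plan's cut-off for women: B >= 50 and F < 50. Appendix 2 flag for women: F < 50.

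| Woman, B to F | Shift row | Decrease row | New onset below 50 | Appendix 2 flag |
|---|---|---|---|---|
| 52 to 48 | no | no (4) | yes | yes |
| 60 to 45 | no | no (15) | yes | yes |
| 51 to 41 | no | no (10) | yes | yes |
| 69 to 49 | no | yes (20) | yes | yes |
| 52 to 39 | yes | no (13) | yes | yes |
| 45 to 38 | yes | no (7) | no, already low | yes |

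The first three women become low and meet neither HDL row. The last is counted as a new shift although she was already below 50. The Appendix 2 column is yes throughout, so it cannot tell the last woman from the others.

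**2. Is new onset shown elsewhere?** The Appendix 2 HDL criterion and the metabolic-syndrome HDL component use only the post-baseline value. Mean change in serum chemistry (CT-10.3.1) uses baseline but gives no incidence. No other planned categorical output conditions HDL on baseline.

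**3. Sensitivity, all inputs assumed.** B and F are taken as bivariate normal with equal SD s and correlation 1 - c²/(2s²), where c is the SD of change. There is one post-baseline value, since Protocol Table 1.3-1 schedules laboratory tests only at screening/baseline and Week 12/ET. The grid is mean 50, 55 or 60; s = 12 or 15; c = 4, 6, 8, 10 or 12; mean change 0, -3 or -6. That is 3 x 2 x 5 x 3 = 90 scenarios, with 2,000,000 simulated women in each.

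- Newly low: N = P(B >= 50, F < 50).
- Missed by the shift row: P(B >= 50, 40 <= F < 50) / N.
- Missed by both rows: P(B >= 50, 40 <= F < 50, B - F < 20) / N.

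One scenario in full: mean 55, s = 15, c = 8, mean change -3. The correlation is 1 - 64/450 = 0.858. N = 12.8% of women; 85.0% of these are missed by the shift row and 81.5% by both rows. That is 0.128 x 0.815 = 10.4% of all women.

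Across the grid:

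| Quantity | Range |
|---|---|
| Women newly below 50 (N) | 3.4% to 27.8% |
| Of these, missed by the shift row | 61% to 99.6% |
| Of these, missed by both HDL rows | 51% to 99.6% |
| Of women the shift row counts, already below 50 at baseline | 39% to 99% |

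The share missed by both rows is lowest when change is most variable and the mean fall largest (c = 12, mean change -6). It is highest when change is small. Numerical integration of the same model agrees with these two ends to within about half a percentage point.

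The share of women starting between 40 and 50 is Φ((50 - m)/s) - Φ((40 - m)/s), where m is the assumed mean. With m = 60, s = 12 it is 0.202 - 0.048 = 15%; with m = 50, s = 12 it is 0.500 - 0.202 = 30%. These are the extremes of the grid.

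**The case against.** The strongest reply is that the shift table has its own categories and need not copy Appendix 2. Glucose supports this: Appendix 2 and the metabolic-syndrome table use 100 mg/dL fasting, yet the glucose shift rows all target 126 or more. Several triglyceride rows target 200 to below 500 although Appendix 2 uses 150. A single HDL cut-off of 40 could likewise be deliberate, so the text does not prove that 40 is an error. What this does not answer is the label. The shift table calls glucose of 100 to below 126 impaired and triglycerides of 150 to below 200 borderline. Only for HDL in women does it call normal a value that the same section calls low.

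A reader might also infer more than the documents support:

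- **That most women who newly become low go unreported.** No document gives an HDL mean, SD or expected change. A narrower set of assumptions (mean 55-60, SD 14-15, change SD 6-8, mean change 0 to -3) gives 80% to 95% missed by both rows, but the wider grid reaches down to about half. Nor are these women unreported: every fasting value below 50 is flagged in CT-10.2.1 to CT-10.2.3 and scores the metabolic-syndrome component, and falls of 20 or more meet the second HDL row.
- **That every woman is affected.** A woman at 50 or above at both times, one below 40 at baseline, or one falling from 50 or more to below 40 is classified alike under either cut-off.
- **That CT-10.5.1.1 will contradict CT-10.2.3 and CT-10.5.3.1.** Those outputs have no baseline HDL condition, and metabolic syndrome needs three or more components. They answer different questions and would differ even after the fix.

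**Conclusion.** The inconsistency is plain in the text and needs no assumption. As written, the HDL rows of CT-10.5.1.1 and CT-10.5.1.2 omit women who fall from 50 or more to between 40 and 50 by less than 20 mg/dL. They also treat women starting between 40 and 50 as normal. The gap is specific: no planned categorical output gives new-onset low HDL in women at the cut-off the SAP uses elsewhere.

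Its size cannot be read from the documents. The range of about 51% to 99.6% of newly low women meeting neither row holds only under the assumed distributions above, and the number of women is unknown. The consequence is modest: one descriptive secondary safety table and its listing. The primary endpoint, frequency and severity of adverse events, is untouched.

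**What to change.** In the lipid criteria of SAP 9.2.2:

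- Make the HDL shift sex-specific, in line with Appendix 2: men from 40 or more to below 40; women from 50 or more to below 50. Use as denominator those at or above the relevant cut-off at baseline.
- Keep the row for a decrease of 20 mg/dL or more.
- Keep the common row, 40 or more to below 40, as a separately labelled row without the word normal. Simply replacing it would lose women who go from between 40 and 50 to below 40, such as 45 to 38, whom the plan now counts.

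If the sponsor prefers the common cut-off alone, the SAP should give the reason and footnote CT-10.5.1.1 accordingly; the new-onset count for women would then remain missing.

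The cost is one extra row and a sex condition in the programming, with no new data collection. The reported incidence of low HDL in women may be higher.

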8.7.2 Physical Examination

Physical examinations will be performed at the time points described in the schedule of assessments (Table 1.3-1).

A complete physical examination will consist of measurement of height and waist circumference and a review of the following body systems: head, eyes, ears, nose, and throat; thorax; abdomen; urogenital; extremities; neurological; and skin and mucosa. At screening/baseline, height will be measured with a stadiometer, measuring stick or tape. Repeat measurement of height is not required at the physical examinations scheduled for the Week 12/early termination (ET) visit. Waist circumference will be measured at each physical examination (screening/baseline and Week 12/ET), using the provided measuring tape. The following procedures will aid in the standardization of these measurements:

- The subject should be minimally clothed (ie, lightweight clothing; no heavy overgarments).
- Waist circumference should be recorded before a subject's meal and at approximately the same time at each visit.
- Measurement will be accomplished by locating the upper hip bone and the top of the right iliac crest and placing a weighted measuring tape in a horizontal plane around the abdomen at the level of the crest. Before reading the tape measure, the assessor should assure that the tape is snug, but does not compress the skin, and is parallel to the floor. The measurement is to be made at the end of a normal exhalation.²⁴

The investigator (or designee) is responsible for performing the physical examination. If the appointed designee is to perform the physical examination, he or she must be permitted by local regulations and his or her name must be included on the delegation of authority log. Whenever possible, the same individual should perform all physical examinations. Any condition present at the post-treatment physical examination that was not present at the baseline examination should be documented as an AE and followed to a satisfactory conclusion.

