10.6 Appendix 6: Criteria for Identifying Vital Signs of Potential Clinical Relevance

Variable	Criterion Value ^a	Change Relative to Baseline ^a
Heart rate ^b	> 100 bpm < 50 bpm	≥ 10 bpm increase ≥ 10 bpm decrease
Systolic blood pressure ^b	≥ 140 mmHg Supine < 90 mmHg	≥ 20 mmHg increase ≥ 20 mmHg decrease
Diastolic blood pressure ^b	≥ 90 mmHg Supine < 60 mmHg	≥ 10 mmHg increase ≥ 10 mmHg decrease
Orthostatic hypotension	≥ 30 mmHg decrease in systolic blood pressure and/or a decrease of ≥ 20 mmHg in diastolic blood pressure after at least 3 minutes of standing compared to the previous supine blood pressure.	Not applicable (baseline status not considered)
Orthostatic tachycardia	≥ 25 bpm increase in heart rate from supine to standing	Not applicable (baseline status not considered)
Weight	—	≥ 7% increase ≥ 7% decrease

bpm = beats per minute.

^aIn order to be identified as potentially clinically relevant, an on-treatment value must meet the “Criterion Value” and also represent a change from the subject’s baseline value of at least the magnitude shown in the “Change Relative to Baseline” column.

^bAs defined in “Supplementary Suggestions for Preparing an Integrated Summary of Safety Information in an Original New Drug Application Submission and for Organizing Information in Periodic Safety Updates,” FDA Division of Neuropharmacological Drug Products draft (2/27/87).

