Appendix 1 Criteria for Identifying Vital Signs of Potential Clinical Relevance

Variable	Criterion Value ^a	Change Relative to Baseline ^a
Heart Rate ^b	> 120 bpm < 50 bpm	≥ 15 bpm increase ≥ 15 bpm decrease
Systolic Blood Pressure ^b	> 180 mmHg < 90 mmHg	≥ 20 mmHg increase ≥ 20 mmHg decrease
Diastolic Blood Pressure ^b	> 105 mmHg < 50 mmHg	≥ 15 mmHg increase ≥ 15 mmHg decrease
Orthostatic Hypotension	≥ 20 mmHg decrease in systolic blood pressure and a ≥ 25 bpm increase in heart rate from supine to sitting/standing	Not Applicable (baseline status not considered)
Weight	-	≥ 7% increase ≥ 7% decrease

^a In order to be identified as potentially clinically relevant, an on-treatment value must meet the “Criterion Value” and also represent a change from the subject’s baseline value of at least the magnitude shown in the “Change Relative to Baseline” column.

^b As defined in “Supplementary Suggestions for Preparing an Integrated Summary of Safety Information in an Original NDA Submission and for Organizing Information in Periodic Safety Updates,” FDA Division of Neuropharmacological Drug Products draft (2/27/87).

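### The blood-pressure component of metabolic syndrome (SAP 9.2.2) requires systolic and diastolic pressure to be raised together, with no reason given, so an isolated elevation does not count

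*SAP*

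**What the plan says.** SAP 9.2.2 announces an incidence summary: "metabolic syndrome will be summarized by parent study treatment group using the following criteria". The table lists five components: waist circumference, triglycerides, HDL, supine blood pressure and fasting glucose. The syndrome row reads "Met 3 Or More of the Above Criteria at a Visit". The blood-pressure row reads "Systolic $\geq 130\text{mmHg}$ and Diastolic $\geq 85\text{mmHg". No footnote qualifies it. The protocol has no metabolic-syndrome definition to fall back on, and SAP section 1 says that the SAP prevails where the two documents differ.

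The vital-sign criteria are built differently. In SAP Appendix 1 systolic pressure has its own row ("> 180 mmHg < 90 mmHg") and so does diastolic ("> 105 mmHg < 50 mmHg"). Protocol Appendix 6 also has separate rows ("≥ 140 mmHg Supine < 90 mmHg" and "≥ 90 mmHg Supine < 60 mmHg"). In both appendices a high or low value must also show a minimum change from baseline, but neither pressure depends on the other.

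**The concern.** A programmer following the SAP would code a joint condition. A supine reading of 185/84 mmHg with a systolic rise of 20 mmHg is potentially clinically relevant under both appendices, yet it fails a metabolic component whose limits are only 130 and 85 mmHg.

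Safety is the only visible objective of the trial, and metabolic syndrome has its own incidence table and listing (CT-10.5.3.1 and CT-10.5.3.2). A component that is stricter than intended makes that table less sensitive. Other tables close only part of the gap. Under SAP Appendix 1, a systolic value from 130 up to 180 mmHg with diastolic below 85 mmHg enters neither the metabolic component nor the incidence of vital-sign abnormalities; it shows only in the mean changes.

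**Working it through.** The plan states no expected syndrome rate, blood-pressure distribution or sample size, so there is no figure of its own to reproduce.

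**1. When the component can be judged.** Protocol 8.7.2 says: "Waist circumference will be measured at each physical examination (screening/baseline and Week 12/ET". Table 1.3-1 also schedules laboratory tests only at screening/baseline and Week 12/ET. Of the five components, only blood pressure is scheduled at Weeks 2, 4 and 8. On scheduled data, three components at one post-baseline visit can therefore be reached only at Week 12/ET, and the blood pressure at that visit decides the component.

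**2. One subject.** Take 145/80 mmHg, triglycerides 160 mg/dL and fasting glucose 105 mg/dL, with waist and HDL not meeting their criteria.
- As written: triglycerides 1 + glucose 1 + blood pressure 0 = 2, not counted.
- Either/or: 1 + 1 + 1 = 3, counted.

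**3. All patterns.** There are six yes/no conditions (waist, triglycerides, HDL, glucose, systolic ≥ 130, diastolic ≥ 85), so 2^6 = 64 patterns. Among the four non-pressure components, 5 patterns have three or more met (4 + 1) and 6 have exactly two met. Each combines with 4 pressure states.
- Joint rule: 5 × 4 + 6 × 1 = 26 patterns count.
- Either/or: 5 × 4 + 6 × 3 = 38 patterns count.
- Difference: 6 × 2 = 12, all with exactly two other components and one raised pressure. None moves the other way.

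The 12 of 64 is a count of patterns, not a proportion of subjects.

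**4. Size for the component (all inputs assumed).** Supine pressures are taken as bivariate normal with means m, SDs s and correlation r.
- P(S) = 1 − Φ((130 − m_S)/s_S)
- P(D) = 1 − Φ((85 − m_D)/s_D)
- P(either) = P(S) + P(D) − P(both)

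At means 122/77, SDs 13/9 and r = 0.6: P(S) = 0.269, P(D) = 0.187, P(both) = 0.115 and P(either) = 0.342. The joint rule captures 0.115/0.342, about 34%.

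Over means 118-126 and 75-79, SDs 12-14 and 8-9, and r 0.5-0.7, fully crossed, the captured share runs from 19% (126/75, SDs 14/8, r = 0.5) to 44% (126/79, SDs 12/9, r = 0.7).

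**5. Size for the syndrome (further assumptions).** With the other four components treated as independent of one another and of blood pressure:

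Syndrome rate = P(three or more others) + P(exactly two others) × P(blood-pressure component)

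Reduction = P(exactly two others) × [P(either) − P(both)]

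Assumed rates for waist/triglycerides/HDL/glucose are 0.30/0.20/0.25/0.20 (exactly two: 0.197; three or more: 0.043) or 0.45/0.30/0.35/0.30 (0.313; 0.124). Pressure means are 115/74, 120/77 or 125/80, with SDs 13/9 and r 0.5-0.7. On this second grid the captured share is 21-47%.

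| Case | P(both) | P(either) | Syndrome, joint | Syndrome, either/or | Reduction |
|---|---|---|---|---|---|
| Smallest: 115/74, r = 0.7, lower rates | 0.057 | 0.178 | 5.4% | 7.8% | 0.197 × 0.121 = 2.4 points |
| Largest: 125/80, r = 0.5, higher rates | 0.170 | 0.469 | 17.7% | 27.1% | 0.313 × 0.299 = 9.4 points |

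**6. A feature that works the other way.** The lipid and glucose table in SAP 9.2.2 has a baseline column. The metabolic-syndrome table has only post-baseline limits and does not require absence at baseline. A subject who already had the syndrome can therefore be counted as treatment-emergent. The documents do not allow this to be sized.

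**The case against.** The strongest reply is that the appendices flag single vital signs, each with a change-from-baseline condition, while this row is one part of a five-part composite. A composite may ask for both pressures without contradicting them. The appendices are also a weak standard, since their own limits differ (systolic ≥ 140 against > 180 mmHg; diastolic ≥ 90 against > 105 mmHg). This stands. A reader might infer that the plan itself proves either/or to be the right definition. It does not: the SAP cites no source for its definition. The documents show only that the joint rule is stricter, unexplained and out of line with how the pressures are handled elsewhere.

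The 'and' may also be loose wording. In SAP 9.4 the QTc category headings join the limits for men and women with 'and', and the definitions beside them switch to 'or'. The blood-pressure cell may likewise just list two limits. That makes the intent unclear but does not remove the problem, because no definition beside this cell settles it.

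The practical weight is limited. Metabolic syndrome is not among the visible protocol endpoints. Weight, waist, BMI, lipids, glucose and mean blood pressure each have their own tables. The rule applies alike to every parent-study group. All of this is correct, and it keeps the point at the level of a secondary safety summary.

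**Conclusion.** The point holds in limited form. As written, an isolated systolic or diastolic elevation does not meet the component, and nothing in either document explains or relaxes this. The direction against an either/or component is certain: the joint rule can never give a higher syndrome count, and it gives a lower one whenever a subject has exactly two other components and one raised pressure.

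The size is illustrative only. About 19-44% of subjects with either value raised would be captured, and the syndrome rate would be roughly 2-9 percentage points lower. Both ranges rest on assumed distributions, and the second also on assumed, independent component rates. The 19-44% describes the blood-pressure component and should not be read as the loss in syndrome cases.

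A reader might infer that the reported treatment-emergent incidence is simply understated. The documents do not support that: with no requirement of absence at baseline, pre-existing cases can raise the count, so the net error is not determined.

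**What to change.** In the SAP 9.2.2 table, change the component to supine systolic ≥ 130 mmHg or diastolic ≥ 85 mmHg. If the joint rule is deliberate, say so, justify it, and add the either/or count as a sensitivity row in CT-10.5.3.1.

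The cost is one word in the SAP, or one sentence and one extra row, with about one line of code. The reported incidence may be higher. No assessment or data collection changes, and the primary adverse-event analysis is unaffected.
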